## 2. EVALUATION CRITERIA

### 2.1. Demographic and other baseline characteristics

Demographic parameters are age, sex, body weight, height, and body mass index (BMI). BMI is calculated, when body weight and height are available, as follows:

$$BMI = \frac{BodyWeight (Kg)}{Height (m)^2}$$

Other baseline characteristics are:

- Subjects' medical history,
- Therapeutic/Palliative strategy at enrolment,
- Prior/concomitant medications at enrolment.

### 2.2. Efficacy criteria

Efficacy criteria are the following assessments:

- Target obliteration per lesion evaluated before the first procedure according to 4 level-score: 1. <50%; 2. 50-75%; 3. 75-99%; and 4. 100% corresponding to a complete nidus obliteration rate,
- Post-procedure obliteration per lesion evaluated after each procedure according to the same 4 level-obliteration-score,
- Successful lesions embolization expressed as the lesions achieving the targeted percentage of obliteration.

### 2.3. Safety criteria

#### 2.3.1. Primary criterion

The primary evaluation criterion is the number and percentage of subjects experiencing adverse drugs reactions (ADRs) occurring during the course of each vascular embolization procedure after administration of Lipiodol® Ultra Fluid in association with surgical glues (e.g. the mixture) and before catheterization laboratory discharge.

All adverse events (AEs) assessed as related to the mixture of Lipiodol® Ultra Fluid and surgical glues will be qualified as ADRs.

#### 2.3.2. Secondary Safety Criteria

Secondary criteria included to support the primary endpoint are the following:

- ADRs from the first administration of Lipiodol® Ultra Fluid in association with surgical glues up to the end of follow-up period,
- The complete set of AEs collected during the study, regardless of causal relationship assessments, from written informed consent until end of the follow-up period.

### 2.4. Other criteria

Not Applicable.

CONFIDENTIAL	STATISTICAL ANALYSIS PLAN N° LUF-44-001  VERSION N° 2.0	Page 8 / 29
--------------	---	-------------

### 3. STATISTICAL METHODS

#### 3.1. General considerations

After the database lock, the statistical analysis will be performed [REDACTED] under the supervision of Guerbet on the basis of the present document. A quality control of the statistical analysis will be performed by the CRO to ensure the reliability of the results prior to providing the results to Guerbet.

Tabulations of quantitative parameters will include the following summary statistics: Number of Subjects / Mean / Standard Deviation (SD) / Minimum / Median / Maximum. The mean and median will be reported to 1 decimal more than the data; SD to 2 more decimals than the data; and minimum and maximum to the same number of decimals as the data.

Tabulations of frequencies for categorical data will include all possible categories and will display the number of observations in a category as well as the percentage (%) relative to the respective group. Percentages will be rounded to one decimal place. The category missing will be displayed only if there are actually missing values. Percentages will be calculated on the total of non-missing recorded categories.

Duration will be computed as follows:

$$(\text{End Date} - \text{Start Date}) + 1 \text{ day(s)}$$

Of note, duration of AEs with same “Start Date” and “End Date” will be listed as “< 1 day”.

Time interval between two events (for example, visits, assessments, ...) will be computed as follows:

$$\text{Date of Event 2} - \text{Date of Event 1} \text{ day(s)}$$

The baseline value will be defined as the last available value prior to the first administration of the investigational product.

All outputs will be produced using SAS® version 9.4 or a later version.

#### 3.2. Null and alternative hypothesis

No specific hypothesis can be set up and no statistical test are planned (see 3.3 for justification).

#### 3.3. Determination of sample size

According to Guerbet best knowledge of the use of Lipiodol® Ultra Fluid along with glues in embolization procedure, no particular safety signal with a related incidence could lead to design a safety study with a specific sample size. Therefore, the number of subjects for the study is based on the requirement of 125 subjects as specified by SEC radio-diagnostic on January 19th, 2017.

#### 3.4. Adjustment for covariates

Not applicable.

#### 3.5. Handling of dropouts or missing data

No imputation will be performed in this trial.

CONFIDENTIAL	STATISTICAL ANALYSIS PLAN N° LUF-44-001  VERSION N° 2.0	Page 9 / 29
--------------	---	-------------

### **3.6. Interim analyses and data monitoring**

No formal interim analysis was planned. Nevertheless, a Data Safety Monitoring Board (DSMB) will be set up within Guerbet including a safety physician, Guerbet medical expert and the clinical project manager. This DSMB will review the following monitored data on a quarterly basis as a minimum:

- AEs and SAEs,
  - Fatal SAE as soon as it is reported,
  - Any reason (adverse event or completion of the treatment/palliative strategy) of any new therapeutic / palliative procedure administration within the follow-up period.
- 

### **3.7. Multicenter studies**

The number of patients included in each center will be displayed in a disposition table.

### **3.8. Multiple comparisons/Multiplicity**

Not applicable as no statistical tests are planned.

### **3.9. Use of an “efficacy subset” of subjects**

Not applicable.

### **3.10. Active control studies intended to show equivalence**

Not applicable.

### **3.11. Examinations of subgroups**

Not applicable.

CONFIDENTIAL

STATISTICAL ANALYSIS PLAN N° LUF-44-001

VERSION N° 2.0

DATED: JUNE 30, 2021

Page 10 / 29

CONFIDENTIAL

STATISTICAL ANALYSIS PLAN N° LUF-44-001

Page 11 / 29

VERSION N° 2.0

DATED: JUNE 30, 2021

CONFIDENTIAL	STATISTICAL ANALYSIS PLAN N° LUF-44-001  VERSION N° 2.0	Page 12 / 29
--------------	---	--------------

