The decision to proceed with a procedure of vascular embolization and the choice of embolization material(s) depends greatly on the patient's clinical presentation, the vascular architecture and size of the lesion(s) and the clinical objectives (reduction of hemorrhagic risk, blood flow redistribution, palliative treatment of unresectable malignant tissues etc.).

Lipiodol® Ultra Fluid is an iodinated oily contrast which has been used for arterial chemoembolization of hepatic tumors since the early eighties [4; 5]. It has since been used in combination with surgical glues at various ratios for endovascular embolization of vascular anomalies such as aneurysms, fistulas or vascular neoplasms [6; 7; 8].

The usefulness of Lipiodol® Ultra Fluid added to surgical glues in this indication is four fold: (i) it increases the polymerisation time hence limiting risks of clogging of the catheters (ii) it permits to adjust the viscosity of the embolic mixture to the lesion angioarchitecture and to the blood flow; (iii) it possesses a transient plastic embolic ability by slowing arterial circulation and adjusting to the size of small nidus vessels [9]; (iv) it allows the fluoroscopic visualization of the embolic mixture due to iodine radiopacity.

The present study aims at depicting the safety of Lipiodol® Ultra Fluid in association with surgical glues in the routine medical practice of transarterial vascular embolization using this association of products as embolization agents. Subjects with a large range of clinical conditions and target lesions are expected to be included.

Guerbet    CONFIDENTIAL	Protocol No. LUF-44-001 Version No. 3.0 Date January 20 th 2017	Page 14 / 43
--	--	--------------

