### 3 STUDY DESIGN

#### 3.1 Protocol Description

This study is a phase IV, multicenter (8 to 10 sites in India), open label, single arm, post-marketing study.

The study is designed to investigate the safety of Lipiodol® Ultra Fluid in association with surgical glues used according to each site medical practice of vascular embolization. Subjects will be enrolled with the main condition that a procedure of vascular embolization using Lipiodol® Ultra Fluid in association with surgical glues is part of their therapeutic/palliative strategy for their disease. The vascular embolization using Lipiodol® Ultra Fluid in association with surgical glue will be administered as study procedure. According to the patient need and health status a second vascular embolization using Lipiodol® Ultra Fluid in association with surgical glue may be considered by the investigator within the next 30 days after the first one. In this case, this procedure will be considered as a second study procedure. The per-procedure safety evaluation will be enabled by appropriate records of safety events during the time frame of the procedure of vascular embolization using Lipiodol® Ultra Fluid in association with surgical glues. Safety evaluation will be completed with safety records within 30 +/-3 days after the embolization procedure. Efficacy evaluation will rely on the level of lesion(s) obliteration after embolization compared to the pre-procedural target level of obliteration. Exploratory descriptive statistical methods will be used to evaluate safety and efficacy, using both the total population and subsets of subjects with similar clinical conditions.

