### 5.5. Efficacy evaluation

All efficacy analysis will be conducted using the TS. Descriptive statistics will be summarized per lesion and per procedure (if applicable) on all available efficacy data.

The following parameters will be presented:

- Number and frequency of the target obliteration scores defined before any procedure,
- Number and frequency of the post-procedure obliteration scores (including for the lesions not targeted initially),
- Number and frequency of lesions embolization.

These analyses will be repeated according to the surgical glue (Histoacryl®, Endoacryl®, Other) associated to Lipiodol® Ultra Fluid.

In case of second procedure, the following analyses will be presented:

- Summary statistics (number [n], mean, standard deviation [SD], median, minimum, and maximum) will be calculated for the number of lesions to be treated with the mixture,
- Number and frequency of the variable "number of lesions to be treated" categorized in class will be also tabulated (1 lesion, 2 lesions, 3 lesions and > 3 lesions),
- The main (up to three) and new lesions to be treated with the mixture will be described in terms of location and type, separately. Summary tables (number and % of subjects) will be tabulated. Description will be also presented by lesion (number and % of lesions).

Listings of all efficacy data will be presented in CSR appendix 16.2.6.

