#### 5.6.2.1 Primary analysis of the primary criteria

The following parameters will be described on ADRs occurring, per study procedure, after administration of Lipiodol® Ultra Fluid in association with surgical glues and before catheterization laboratory discharge (i.e

CONFIDENTIAL	STATISTICAL ANALYSIS PLAN N° LUF-44-001  VERSION N° 2.0	Page 18 / 29
--------------	---	--------------

ADR start date is greater or equal to time of first injection and lower or equal to time leaving the catheterization laboratory):

- Number and percentage of subjects experiencing at least one ADR,
- Number of ADRs,
- Distribution of number of ADRs per subject (1/2/3 or more),
- Number and percentage of subjects presenting with at least one ADR per intensity,
- Number of ADRs according to their intensity,
- Number and percentage of subjects presenting with at least one ADR per outcome,
- Number of ADRs according to their outcome,
- Number and percentage of subjects presenting with at least one ADR requiring an ADR-targeted medication,
- Number of ADRs requiring an ADR-targeted medication,
- Number and percentage of subjects presenting with at least one ADR requiring another ADR-targeted action,
- Number of ADRs requiring another ADR-targeted action,
- Number and percentage of subjects presenting with at least one ADR per lesion location,
- Number of ADRs per lesion location,
- Number and percentage of subjects presenting with at least one ADR per lesion type,
- Number of ADRs per lesion type,
- Number and percentage of subjects with mixture administration withdrawal due to at least one ADR,
- Number of ADRs leading to discontinuation of mixture administration,
- Number of ADRs leading to premature discontinuation,
- Number and percentage of subjects presenting with at least one serious ADR, whatever the seriousness criteria,
- Number of serious ADRs, whatever the seriousness criteria,
- Number and percentage of subjects presenting with at least one serious ADR per seriousness criteria,
- Number of serious ADRs per seriousness criteria.

The following distributions, by SOC and PT, will be tabulated on ADRs occurring, per study procedure, after administration of Lipiodol® Ultra Fluid in association with surgical glues and before catheterization laboratory discharge (i.e ADR start date is greater or equal to time of first injection and lower or equal to time leaving the catheterization laboratory):

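### Protocol 3.1 commits to results in clinically similar subsets, but SAP 3.11 sets subgroups to not applicable and the visible SAP splits efficacy only by glue brand

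*SAP*

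**What the plan says.** Protocol 3.1 commits the study to describing safety and efficacy "using both the total population and subsets of subjects with similar clinical conditions". Protocol 1 gives the reason: "Subjects with a large range of clinical conditions and target lesions are expected to be included". Protocol 12 leaves the full description of methods to the SAP.

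SAP 3.11, under the heading "Examinations of subgroups", is marked not applicable.

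For efficacy, SAP 5.5 sets the unit of analysis: "Descriptive statistics will be summarized per lesion and per procedure (if applicable) on all available efficacy data". It names one stratifier: "These analyses will be repeated according to the surgical glue (Histoacryl®, Endoacryl®, Other) associated to Lipiodol® Ultra Fluid".

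For safety, SAP 5.6.2.1 goes further. It asks for "Number and percentage of subjects presenting with at least one ADR per lesion location", for "Number of ADRs per lesion type", for the matching event and subject counts, and for a repeat by glue. SAP 5.6.2.4 repeats that analysis for the period after discharge from the catheterization laboratory and for the whole period from first administration.

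**The concern.** The protocol admits arterial, venous and arteriovenous malformations, fistulas, and benign and malignant vascular tumours (Protocol 4.1, inclusion criterion 2). A single obliteration or success table over such a mix is hard to interpret, and the subset clause in Protocol 3.1 answers that difficulty. The document that should put the clause into effect instead sets subgroups aside without giving a reason, and for efficacy it substitutes glue brand, which is not a clinical condition. If the visible SAP is followed as written, the report will have no efficacy result for any group of clinically similar subjects, although the data to produce one are collected.

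**Working it through.** **Is there a figure to reproduce?** No. No hypothesis or test is planned, and the sample size of 125 is a regulatory requirement (Protocol 8, SAP 3.3). The check is a comparison of texts, with two illustrations and a denominator example based on assumed inputs.

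**Step 1: is the commitment still in force?** The subset clause stands in Protocol 3.1. The synopsis describes the same methods without it, and Protocol 12.1 to 12.5 neither repeat nor define it. Nothing in the protocol or the visible SAP withdraws it.

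**Step 2: what does the visible SAP deliver?**

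| Result | By lesion type | By lesion location | By glue |
|---|---|---|---|
| ADRs (SAP 5.6.2.1, repeated in 5.6.2.4) | yes | yes | yes |
| Target and post-procedure obliteration, lesion embolization (SAP 5.5) | no | no | yes |

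SAP 5.5 does mention location and type for a second procedure, but only to describe which lesions are to be treated, not their obliteration results. The first row contradicts the entry in SAP 3.11. The second row is the gap against Protocol 3.1.

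**Step 3: are the data there?** Lesion type and location are recorded at enrolment (Protocol 9.1) and tabulated at baseline for up to three main lesions (SAP 5.4.2). Obliteration is scored per lesion (Protocol 9.2 and 9.3). The missing tables need no new data collection for those lesions.

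**Step 4: what does pooling do?** Assume success of 60% in lesion type A and 90% in type B; neither rate is in the documents.
- A:B = 2:1 gives (2×60 + 90)/3 = 70%
- A:B = 1:1 gives (60 + 90)/2 = 75%
- A:B = 1:2 gives (60 + 2×90)/3 = 80%

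The pooled figure moves by 10 points with no change in either type.

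**Step 5: would subset tables be informative?** The documents give no subset sizes. Assume 80% success and independent lesions. The exact (Clopper-Pearson) 95% interval is 71.9% to 86.6% for 100/125 and 59.3% to 93.2% for 20/25. Subset tables are feasible but wide, so they can only describe.

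**Step 6: the ADR split in subjects with several lesions.** The AE items in Protocol 10.1.3 and the listings in SAP 5.6.2.4 and 5.6.3 show no lesion. The lesion is recorded per injection, but only the first injection is timed (Protocol 9.2 and 9.3), so onset time cannot tie an event to one of several treated lesions. The denominator for the lesion rows is also open. As an assumed example, 3 subjects with an ADR among 30 with a given location, with 125 treated, give 3/125 = 2.4% or 3/30 = 10%.

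**The case against.** The best defence is that the subset phrase is one clause in a design narrative. The synopsis omits it, the protocol's statistical section specifies no subsets, and similar clinical conditions are never defined. This is also primarily a safety study, and its primary criterion is tabulated by lesion location and type. Success is judged against each lesion's own target, so the endpoint is already individualised to some degree. All of this is fair, and it limits the point to efficacy. It does not remove the conflict: Protocol 12 hands the detail to the SAP, and the SAP answers with not applicable.

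A reader might infer more than the documents support:

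- That efficacy is not broken down by lesion at all. SAP 5.5 summarises it per lesion; what is absent is a split by lesion type or location.
- That the safety subsets are missing. They are planned in SAP 5.6.2.1 and repeated in 5.6.2.4.
- That the ADR counts by lesion will be wrong, with one event counted up to four times. SAP 5.6.1 does provide for four treated lesions, but no rule is stated and multiple counting is only one possible implementation. Baseline location and type are described for up to three main lesions, a subject with lesions at two sites may properly appear in both rows, and single-lesion subjects raise no difficulty.
- That the SAP is silent on denominators. SAP 3.1 has general percentage rules, and SAP 5.2 and 5.6 set the Treated Set for safety. Only the choice for the lesion rows is unclear.
- That the split appears nowhere in the plan. SAP sections 4 and 6 and the CRF are not available for review, so absence can be stated only for the visible text.

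**Conclusion.** The point holds for efficacy. SAP 3.11 conflicts with Protocol 3.1 and with the SAP's own ADR tables, and on the visible text the protocol's subset description is not delivered for target obliteration, post-procedure obliteration or target achievement. For safety it is largely delivered, and the overall primary ADR percentage does not change.

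The size of the effect on the efficacy results cannot be taken from the documents. The 10-point shift in Step 4 rests on assumed rates and mixes and shows only the mechanism. The conclusion assumes that the unavailable SAP sections contain neither these tables nor a justification for dropping them; if they do, SAP 3.11 should refer to them. The missing rule for ADRs in subjects with several lesions is a secondary clarification and would not carry the point alone.

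**What to change.** 1. In SAP 3.11, replace the current entry with descriptive subsets based on lesion type and lesion location. The protocol does not define similar clinical conditions, so the SAP has to; type and location are a proposal that fits the data collected and the existing ADR tables. List the glue split there too, so that the section agrees with the rest of the SAP.
2. In SAP 5.5, tabulate target scores, post-procedure scores and target achievement (as defined in SAP 2.2) by these subsets. Show counts beside percentages and label the tables descriptive, because some subsets will be small.
3. If the sponsor prefers not to do this, record the departure from Protocol 3.1 and justify it.
4. As a clarification in SAP 5.6.2.1, state how an ADR in a subject with several lesions is assigned to location and type, and whether the denominator is all treated subjects or those with that lesion. One option is a separate class for subjects with multiple types or locations, at the price of losing their detail.

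The cost is SAP wording and a few further tables from data already collected. The drawback is sparse cells, which invite over-reading unless they are labelled.

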## 5. STATISTICAL AND ANALYTICAL PLANS

### 5.1. Disposition of subjects

Subject disposition will be based on all subjects included who have signed their informed consent form (ICF) and tabulated for the following categories:

- Total number of subjects enrolled,
- Total number of subjects exposed (at least one injection of the mixture regardless of the quantity),
- Number (percentage) of subjects by study visit,
- Number (percentage) of subjects completing the study,
- Number (percentage) of subjects prematurely discontinuing from study,
- Primary reason for premature discontinuation.

Of note, If a patient withdrew for Adverse Event and at least one adverse event is coded with PT=< COVID-19 > then the reason of premature withdrawal will be put at COVID-19 but if no AE is coded with PT=< COVID-19 > then the reason of premature withdrawal will be put at Adverse Event other than COVID-19.

Moreover, if a patient withdrew for other reason, then the reason of premature withdrawal will be derived from the specify field as the following:

Specify field of "Other Reason"	Reason of premature withdrawal
"COVID-19 crisis preventing patient to follow protocol schedule"	COVID-19 pandemic preventing patient to follow protocol schedule
"Withdrawal of patient's consent due to Covid-19 pandemic"	Withdrawal of patient's consent due to COVID-19 pandemic
Other	Other reason

Listings of the disposition of subjects will be provided in CSR appendix 16.2.1.

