## STUDY SYNOPSIS

Study Title: Safety and Efficacy of Lipiodol® Ultra Fluid in Association with Surgical Glues during Vascular Embolization, a phase IV study	
EU PAS register number: EUPAS15045	
Study product: Lipiodol® Ultra Fluid (480 mg I/ml), solution for injection	Active Ingredient(s): Ethyl esters of iodized fatty acids of poppy seed oil (Lipiodol® Ultra Fluid)
Planned start date (First Subject In): Q3 2016	Participating countries (Number of sites):
Planned end date (Last Subject Out): Q4 2017	India (Approx. 10 sites)
Study Objectives	
Primary objective: To evaluate the per-procedure safety of Lipiodol® Ultra Fluid in association with surgical glues during vascular embolization in routine medical practice.	
Secondary objectives: 
 
- To evaluate the safety of Lipiodol® Ultra Fluid in association with surgical glues up to one month after the last vascular embolization procedure.
 
- To evaluate the efficacy of Lipiodol® Ultra Fluid in association with surgical glues in vascular embolization.
 
	

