### 7.2 Secondary Criteria

The study will evaluate additional safety criteria:

- ADRs from the first administration of Lipiodol® Ultra Fluid in association with surgical glues up to the end of the follow-up period.
- The complete set of AEs collected during the study, regardless of causal relationship assessments, from written informed consent until end of the follow-up period.

Efficacy will be explored with the following assessments:

- Target obliteration per lesion evaluated before the first procedure according to 4 level-score: 1. <50%; 2. 50-75%; 3. 75-99%; and 4. 100% corresponding to a complete nidus obliteration rate
- Post-procedure obliteration per lesion will be evaluated after each procedure according to the same 4 level-obliteration-score
- Successful lesions embolization, expressed as the lesions achieving the targeted percentage of obliteration

At subject enrolment visit, all lesions designated for vascular embolization using Lipiodol® Ultra Fluid associated with surgical glue will be described on the basis of the most recent angiogram and will be associated to a target percent obliteration (i.e. at least x% obliteration or approximately x% obliteration) that is expected to be reached during the procedure. After the procedure, the percent obliteration will be assessed on earliest available angiogram (e.g. Digital Subtraction Angiography (DSA), Computerized Tomography-Angiography (CTA), Magnetic Resonance Angiography (MRA), vascular imaging Ultrasound (US), Doppler US) consistence with the target obliteration will be provided by the investigator.

Guerbet    CONFIDENTIAL	Protocol No. LUF-44-001 Version No. 3.0 Date January 20 th 2017	Page 23 / 43
--	--	--------------

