### 11.2 End of Study Participation for a Subject

End of study participation for a subject should be the end of follow-up for all subjects with at least one administration of mixture of Lipiodol® Ultra Fluid and surgical glue

Criteria for premature discontinuation of subjects:

- Inclusion criteria not met / Non inclusion criteria met
- Adverse Event (according to the investigator's judgement)
- Withdrawal of subject's consent
- Discovery of an unexpected, significant, or unacceptable risk to the subjects enrolled in the study
- At the discretion of the investigator if the subject safety or well-being is not compatible with study continuation
- Cancellation of the scheduled study procedure using Lipiodol® Ultra Fluid associated with surgical glues
- Lost-to-follow-up
- Other reason to be specified

For discontinued subjects, all data available at the time of their premature discontinuation will be reported in the medical file and the CRF (e.g. enrolment data, safety data, administration data if any, reason for discontinuation). The investigator must make every effort to collect and record all follow-up safety information (i.e. adverse events), unless the subject withdraws consent for further data collection for the study.

Discontinued subjects will receive appropriate medical care decided with the treating physicians for their condition.

 CONFIDENTIAL	Protocol No. LUF-44-001 Version No. 3.0 Date January 20 th 2017	Page 33 / 43
---	--	--------------

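### SAP 5.1 labels a withdrawal for an adverse event as COVID-19 whenever the subject has any COVID-19 event, so a subject can be counted under the wrong primary reason

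*SAP*

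**What the plan says.** SAP 5.1 lists the items of the disposition table, among them "Primary reason for premature discontinuation". A note then splits withdrawals for an adverse event into two rows. If "at least one adverse event is coded with PT=< COVID-19 > then the reason of premature withdrawal will be put at COVID-19". The second row, for adverse events other than COVID-19, is used only when none of the subject's events carries that preferred term. The section ends: "Listings of the disposition of subjects will be provided in CSR appendix 16.2.1".

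Three other places bear on the rule:

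- Protocol 7.2 defines the AE criterion as "The complete set of AEs collected during the study, regardless of causal relationship assessments, from written informed consent until end of the follow-up period".
- Protocol 11.2 says of discontinued subjects: "The investigator must make every effort to collect and record all follow-up safety information (i.e. adverse events"). The exception is a subject who withdraws consent to further data collection.
- SAP 5.6.2.1 plans a count headed "Number of ADRs leading to premature discontinuation", and SAP 5.6.2.4 plans the same count for all AEs.

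**The concern.** A primary reason for discontinuation should be the reason. The AE branch of SAP 5.1 replaces it with co-occurrence: one COVID-19 event anywhere in the subject's record decides the row.

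The rest of the plan works differently. In the same section, withdrawals for other reasons are classified from the text that the site recorded. In SAP 5.2, a deviation is set apart as COVID-related when its reason was the pandemic. In SAP 5.6.2, events are counted by whether they led to discontinuation.

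At stake is the accuracy of one descriptive row in a safety study. Provided COVID-19 events are coded to this preferred term, the error goes in one direction only, away from other events and towards a cause unconnected with the product.

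**Working it through.** No figure in the plan depends on this rule, so there is nothing to reproduce. The check applies the rule as written to simple cases and then bounds its size.

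**1. Scope of the rule.** One branch applies if any event has the preferred term COVID-19; the other applies if none has. Together they cover every AE withdrawal, so the rule searches all of the subject's events. It contains no condition on cause or date.

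**2. Can a non-causing COVID-19 event be in the data?** Yes. Protocol 7.2 collects events from consent onwards, so an earlier, resolved infection is recorded. Protocol 11.2 asks for events after discontinuation, and Protocol 14.3.2 expects a one-month follow-up once the mixture has been given. A later infection can therefore be recorded too.

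**3. Four test subjects, all withdrawn for an AE** (the days are illustrative):

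| Subject | Row under SAP 5.1 | Row if tied to the causing AE |
|---|---|---|
| A: COVID-19 event caused withdrawal | COVID-19 | COVID-19 |
| B: other event caused withdrawal on day 10; COVID-19 on day 3, resolved | COVID-19 | AE other than COVID-19 |
| C: other event caused withdrawal on day 10; COVID-19 began on day 20 | COVID-19 | AE other than COVID-19 |
| D: no COVID-19 event | AE other than COVID-19 | AE other than COVID-19 |

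B and C are in the wrong row. The two rows together hold four subjects under either rule, so the total does not move.

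**4. Does another output show the true reason?** For a treated subject, the causing event can be counted in SAP 5.6.2.1 or 5.6.2.4 as leading to discontinuation, and the disposition row can then disagree with it. For a subject withdrawn before treatment there is no such count. The safety tables use the Treated Set and their windows start at first administration. That subject's causing event appears only in the listings.

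**5. Size.** One misplaced subject is 1/125 = 0.8 percentage points, using the 125 subjects of SAP 3.3. The documents give no withdrawal or COVID-19 rates. As an assumption, let w be the proportion withdrawn for a non-COVID AE and c the proportion with an unrelated COVID-19 event, independent of each other. The expected number misplaced is 125 × w × c:

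- w = c = 1%: 125 × 0.01 × 0.01 = 0.0125
- w = c = 5%: 125 × 0.05 × 0.05 = 0.3125

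Both are below one subject even with all 125 exposed to the pandemic.

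**The case against.** The strongest reply is that this hardly matters. The study is descriptive, with no tests. The two rows add up to all AE withdrawals, and the investigator's own reason remains in the medical file and the CRF. The authors may have meant only the causing event, or may have written a programmable stand-in for a link that the database lacks: Protocol 10.1.3 records action taken on the mixture but no event-level field for leaving the study, and the CRF is not among the documents. The late-onset route (subject C) is also narrow, arising mainly for treated subjects who are withdrawn and still followed. All of this stands. It limits the size of the problem and shapes the fix, but it does not make the sentence right.

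Some stronger readings are tempting and are not supported:

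- *The rule hides a product-related safety event.* It does not. The event stays in the listings and, for treated subjects whose event falls in the analysis windows, in the AE and ADR tables. Only the disposition reason is wrong.
- *The chance of an error is substantial.* With w = c = 5% and all 125 at risk, the chance of at least one misplaced subject is 1 − (1 − 0.0025)^125 = 27%. That combines two generous assumptions with full exposure. Participation lasts at most 70 days (Protocol 3.2). The synopsis planned the last subject out for Q4 2017, and COVID-19 appears only in the SAP of June 2021. The number of subjects at risk is unknown.
- *One subject could shift a row by many points.* SAP 3.1 says "Percentages will be calculated on the total of non-missing recorded categories", which might suggest a denominator of discontinued subjects only. With an assumed 5 to 20 of them, one subject would be 20 to 5 points. But SAP 5.1 names no percentage for this item, and no document gives the number discontinued.

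**Conclusion.** The point holds as a minor error of classification. As written, the rule puts a subject withdrawn for another event into the COVID-19 row if any COVID-19 event is on record, and nothing in the visible text narrows it. The likely effect is none or one subject. That is a judgement resting on the assumed rates above and on short participation, not on a documented rate. The 0.8-point figure assumes that the planned 125 is both reached and used as the denominator. The disagreement with SAP 5.6.2 for a treated subject presupposes an event-level link that those counts imply but that cannot be confirmed. The unseen SAP pages are a remaining uncertainty. Changing the sentence is worthwhile but optional.

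**What to change.** Replace the sentence in SAP 5.1 with:

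> If a subject withdrew for Adverse Event, the reason is COVID-19 only if the AE that led to the withdrawal is coded PT COVID-19; otherwise it is Adverse Event other than COVID-19.

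If the database links events to study withdrawal, the cost is this sentence and one changed derivation. If it does not, settle the few AE withdrawals case by case at the data review meeting before database lock; SAP 5.2 already uses the minutes of that meeting for COVID-related deviations. That review is the only downside and is small. No new data are needed and no other analysis changes.
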